## **8.2 SAFETY**

Patients will be evaluable for safety if they have received any partial or complete treatment cycle. All AEs will be graded according to the NCI-CTCAE, v.4 and will be coded using the Medical Dictionary for Regulatory Activities (MedDRA). Cycle delays, skipped doses, dose reduction requirements, and reasons for treatment discontinuation will be monitored throughout the study.

The safety profile of patients will be monitored throughout the treatment and up to 30 days after the last treatment dose (EOT), or until the patient starts a new antitumor therapy or until the date of death, whichever occurs first.

Any treatment-related AEs will be followed until recovery to at least grade 1 or stabilization of symptoms, whenever possible.

## **8.3 PHARMACOKINETICS**

All patients included in the study will be sampled for pharmacokinetics (PK). Twelve PK samples will be obtained on Day 1, 8 and 15 of Cycle 1 and will be evaluated by standard non-compartmental analysis (population pharmacokinetic modeling may be performed if appropriate).

The following parameters will be calculated: AUC,  $C_{max}$ , CL, and half-life ( $t_{1/2}$ ).

The area under the blood concentration-time curve (AUC) will be determined using the log-linear trapezoidal method with extrapolation to infinity using the terminal rate constant  $k$  ( $C_{last}/k$ , where  $C_{last}$  is the last measured analyte concentration). The  $C_{max}$  will be derived directly from the experimental data. The terminal rate constant ( $k$ ) will be estimated by log linear regression analysis of the terminal phase of the blood concentration vs. time curve. The  $t_{1/2}$  will be calculated from the equation  $0.693/k$ ; total blood CL will be determined by dividing the total administered dose by the AUC.

If considered appropriate by the Sponsor, compartmental analysis on the study results will also be performed, and population PK analysis will be made in pooled results of the different studies. If applicable, PK/PD parameters will be correlated.

## **8.4 BIOMARKERS AND EXPLORATORY EVALUATIONS**

Biomarker analyses will look for a correlation of efficacy with molecular markers related to the mechanism of action of plitidepsin or to the pathogenesis of the disease, such as a) alterations in DNA and RNA, including DNA mutational status, RNA expression levels and miRNA expression for common genetic lesions affecting the AITL clone, b) alteration in tumor factors including (but not limited to) assessment of pathways and mechanisms of action of plitidepsin, at the RNA and/or protein expression level, and c) peripheral blood analyses, to identify plasma biomarkers including (but not limited to) cancer-related mutations and to extract DNA. Examples of exploratory evaluations and analyses, whenever relevant and depending on sample availability, include:

- Common genetic lesions affecting the AITL clone: for example, TET2, IDH2, DNMT3A, RHOA, ITK or SYK.
- Transcriptional profile of AITL.

- Microenvironment factors: for example, markers of B cells (CD40, ICOS), endothelial cells (VEGF, Angiopoietin), follicular dendritic cells (CXCL13), and other T-cell subpopulations (IL10, IL21, TGF- $\beta$ ).
- Factors associated with the mechanism of action of plitidepsin: for example, eEF1A2, Rac1 GTPase, JNK/phospho-JNK.
- Predictive and prognostic tissue or plasma biomarkers associated with response to treatment: to identify possible mechanisms of resistance to plitidepsin through the comparative analysis of potential biomarkers in the pretreatment samples, and comparison with the post-progression biopsy tissue samples (when available), and in peripheral blood. For this objective, new representative biopsies in relapsed patients would be optimal.

## **8.5 ADVERSE EVENTS DEFINITIONS**

### **8.5.1 Adverse Event (AE)**

An AE is any untoward medical occurrence in a patient or clinical investigation patient administered a pharmaceutical product which does not necessarily have a causal relationship with this treatment.

An AE can therefore be any unfavorable and unintended sign, (e.g., an abnormal laboratory finding), or a disease temporally associated with the use of a medicinal product, whether or not considered related to the medicinal product.

Illnesses with onset during the study or exacerbations of pre-existing illnesses, including but not limited to clinically significant changes in physical examination findings and abnormal objective test findings (e.g., X-ray, ECG) should be recorded. The criteria for determining whether an abnormal objective test finding should be reported as an AE are as follows:

- The test result is associated with clinically significant symptoms, and/or
- The test result leads to a change in the study dosing or discontinuation from the clinical trial, significant additional concomitant drug treatment or other therapy, and/or
- The test result leads to any of the outcomes included in the definition of a SAE (see definition below), and/or
- The test result is considered to be clinically relevant by the Investigator.

For the purposes of this protocol, disease progression, worsening of the underlying disease or appearance of new tumor lesions, or any sign or symptom clearly related with this circumstance is NOT an AE.

### **8.5.2 Serious Adverse Event (SAE)**

A SAE is any adverse experience occurring at any dose that:

- Results in death (is fatal),
- Is life-threatening,
- Requires or prolongs inpatient hospitalization,
- Results in persistent or significant disability or incapacity,
- Is a congenital anomaly or birth defect,
- Is medically significant, or
- Is any suspected transmission of an infectious agent via a medicinal product.

Medical and scientific judgment should be exercised in deciding whether expedited reporting is appropriate in other situations such as important medical events that may not be immediately life-threatening or result in hospitalization but may jeopardize the patient or may require intervention to prevent one of the outcomes listed in the above definition.

### **8.5.3 Death**

Death as such is the outcome of a SAE and should not be used as the SAE term itself, whenever possible. The cause of death should be recorded as the SAE term instead. When available, the autopsy report will be provided by the Sponsor.

Grade 5 should be used only for events for which there is a causal relationship with the patient's death (e.g. the event was the direct cause of the death). Grade 4 should be used for the events with the outcome of death but there is no causal relationship between them (e.g. the death was not directly caused by the reported event but related to other comorbidities or complications).

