### **8.5.4 Life-threatening Event**

Any event in which the patient was at risk of death at the time of the event is considered life-threatening; it does not refer to an event which hypothetically might have caused death if it were more severe.

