## **8.6 ADVERSE EVENTS REPORTING PROCEDURES**

### **8.6.1 Reporting Adverse Events**

The Sponsor will collect AEs until 30 days after administration of the last dose of study drug(s)/IMP(s) or until the start of a new antitumor therapy, whichever occurs first. All AEs suspected to be related to the study drug/IMP must be followed-up after the time of therapy discontinuation until the event or its sequelae resolve or stabilize at an acceptable level to the Investigator and the Sponsor.

All AEs, including misuse, overdose, abuse and medication error, must be recorded in English using medical terminology in the source document and the e-CRF. Whenever

possible, the Investigator will record the main diagnosis instead of the signs and symptoms normally included in the diagnoses.

Investigators must assess severity (grade) of the event following the NCI-CTCAE v.4 and assign a relationship to each study drug(s)/IMP(s); and pursue and obtain information adequate both to determine the outcome and to assess whether it meets the criteria for classification as a SAE requiring immediate notification to the Sponsor or its designated representative. The Investigator must provide any relevant information as requested by the Sponsor in addition to that on the e-CRF.

Abnormal laboratory tests occurring during the study should only be recorded in the AE section of the e-CRF if the disorder:

- is associated with clinically significant symptoms, and/or
- leads to a change in study dosing or discontinuation from study treatment, significant additional concomitant drug treatment or other therapy, and/or
- leads to any of the outcomes included in the definition of a SAE.

Otherwise, laboratory results should be reported in the corresponding section of the e-CRF (e.g. biochemistry, hematology).

Disease progression or appearance of new tumor lesions, or any sign or symptom clearly related with this circumstance is NOT an AE.

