7.1 Toxicity and adverse events

All the adverse events will be coded using the Medical Dictionary for Regulatory Activities (MedDRA).

The toxicity evaluation will be coded with the National Cancer Institute-Common Terminology Criteria for Adverse Events (NCI-CTCAE), version 4.

As far as all the toxicities are concerned, the NCI-CTCAE grade will be used wherever an NCI-CTCAE grading exists. Otherwise, the severity will be noted. As a convention, the term «Grade» will always be used. Toxicities will be described according to the worst NCI-CTCAE grade or, for toxicities which do not form the subject of NCI-CTCAE classification, according to the worst severity. For “Worst per cycle” calculation purpose, onset and end cycle of each event will be derived.

Summary of overall adverse events will be done by body system and preferred term, by severity (worst toxicity grade) and by relationship to the study drug. Events with unknown relationship will be considered as related events for reporting purposes.

A frequency table will be made for the AEs leading to cycle delay, dose reduction, skipped dose, or withdrawal of study medication. Adverse events with outcome of death will also be presented by relationship to the study drug.

All events entered in Adverse Event form with the onset date before the first drug administration, will be reported as Signs and symptoms. Only those events with start date after/equal the first infusion date will be included in AE tables in Safety section (except those including evolution from baseline).

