12.2 Adverse Events (AEs)

12.2.1 Display of adverse events

Table 12.2.1.1 Summary of adverse events.

	N (%)
Patients with at least one AE regardless relationship	X (X.X)
Any treatment-related AE	
Any grade 3/4 AE	
Any grade 3/4 treatment-related AE	
Any SAE in DB	
Any treatment-related SAE	
Any grade 3/4 SAE	
Any grade 3/4 treatment-related SAE	
AEs leading to death	
AEs treatment-related leading to death	
AEs leading to dose delay	
AEs leading to dose reduction	
AEs leading to treatment discontinuation	
AEs treatment-related leading to treatment discontinuation	

Table 12.2.1.2 Evolution of lymphoma-related AEs at baseline

		Worst grade per patient						Total		
		0		1		...		N	%	
		N	%	N	%	N	%			
Baseline	Fatigue	Grade 0	X	X.X	X	X.X	X	X.X	X	X.X
		Grade 1								
									
	Bone Pain	Grade 0								
		Grade 1								
									
	Myopathy	Grade 0								
		Grade 1								
									

Table 12.2.1.3 Treatment-related* adverse events. Worst grade by patient

	Preferred Term	Grade 1		...	Grade 4		All**	
		N	%	...	N	%	N	%
SOC	Anemia NOS	X	X.X		X	X.X	X	X.X
Blood and lymphatic system disorders	...							
Cardiac disorders	Arrhythmia NOS							
	...							

(* or Unknown relationship (***) Any grade

Table 12.2.1.4 Treatment-related* adverse events. Worst grade by cycle

	Preferred Term	Grade 1		...	Grade 4		All**	
		N	%	...	N	%	N	%
SOC	Preferred Term	N	%	...	N	%	N	%
Blood and lymphatic system disorders	Anemia NOS	X	X.X		X	X.X	X	X.X
	...							
Cardiac disorders	Arrhythmia NOS							
	...							

(* or Unknown relationship (** Any grade

Table 12.2.1.5 Adverse Events regardless of relationship. Worst grade by patient

	Preferred Term	Grade 1		...	Grade 4		All*	
		N	%	...	N	%	N	%
SOC	Preferred Term	N	%	...	N	%	N	%
Blood and lymphatic system disorders	Anemia NOS	X	X.X		X	X.X	X	X.X
	...							
Cardiac disorders	Arrhythmia NOS							
	...							

(* Any grade

Table 12.2.1.6 Adverse Events regardless of relationship. Worst grade by cycle

	Preferred Term	Grade 1		...	Grade 4		All*	
		N	%	...	N	%	N	%
SOC	Preferred Term	N	%	...	N	%	N	%
Blood and lymphatic system disorders	Anemia NOS	X	X.X		X	X.X	X	X.X
	...							
Cardiac disorders	Arrhythmia NOS							
	...							

(* Any grade

Listing 12.2.1.7 Treatment-related* grade 3-4 adverse events. Worst grade by patient

Patient id.	SOC Name	Preferred term	Grade

(* or Unknown relationship

Listing 12.2.1.8 Treatment-related* grade 3-4 adverse events. Worst grade by cycle

Patient id.	Cycle	SOC Name	Preferred term	Grade

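### Protocol 8.5.3 sets Grade 4 from a fatal outcome rather than from severity, contradicting the NCI-CTCAE grading rule, and can only raise the grade 3/4 counts

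*Protocol*

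**What the plan says.** Protocol 8.5.3 divides events by their causal link to the death. For the causal event, "Grade 5 should be used only for events for which there is a causal relationship" with the death. For the rest, "Grade 4 should be used for the events with the outcome of death but there is no causal relationship between them". The example given is a death that traces to other illness or complications and not to the reported event. The sentence does not mention how severe the event was.

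Elsewhere the Protocol grades by severity and states no exception. Section 8.2: "All AEs will be graded according to the NCI-CTCAE, v.4". Section 8.6.1: "Investigators must assess severity (grade) of the event following the NCI-CTCAE v.4". Section 9.2.2 repeats this for both adverse events (AEs) and serious adverse events (SAEs). Section 8.5.4, directly after the disputed text, ties the notion of life-threatening to the moment of the event: "Any event in which the patient was at risk of death at the time of the event is considered life-threatening".

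The SAP uses the grade as recorded. Section 7.1: "Toxicities will be described according to the worst NCI-CTCAE grade". Table 12.2.1.1 has grade 3/4 rows for AEs, treatment-related AEs, SAEs and treatment-related SAEs. For fatal events, SAP 7.1 says: "Adverse events with outcome of death will also be presented by relationship to the study drug". Table 12.2.1.1 adds a row labelled "AEs leading to death", and Listing 12.3.2.3 covers deaths from AEs. The SAP does not say whether that row and that listing are selected by outcome or by Grade 5.

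**The concern.** A grade should describe the event. Under 8.5.3, two events of the same severity receive different grades if one is coded with a fatal outcome and the other is not, even though neither caused a death. A site cannot follow both 8.5.3 and 8.6.1 for a mild event coded this way.

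Safety is a secondary objective, and its main summaries are counts by grade. There is no randomized comparison (Protocol 5.7), so no control arm is recorded under the same rule and the single-arm rates are read at face value. Disease progression is not an AE in this protocol (8.5.1, 8.6.1), so when a patient dies of lymphoma the cause of death is not itself on the AE form. SAP 7.1 also reports events of unknown relationship as related, so a non-causal event with that coding would reach the treatment-related rows as well.

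A second, separate exposure concerns the fatal-event displays. Section 8.5.3 accepts that an event can carry an outcome of death without having caused it, and SAP 7.1 selects on that outcome.

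**Working it through.** No figure in the documents depends on this rule, so there is nothing to reproduce. The check sets the texts side by side and then follows an event from its true grade to the tables.

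**1. What fixes the grade**

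| Source | What fixes the grade |
|---|---|
| Protocol 8.2, 8.6.1, 9.2.2 | NCI-CTCAE v.4 severity, all AEs |
| Protocol 8.5.3, causal event | Grade 5 |
| Protocol 8.5.3, non-causal event with fatal outcome | Grade 4, whatever the severity |

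The first and third rows agree only if the event's true grade happens to be 4. Section 8.5.3 is not written as an exception to the other sections.

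**2. Scope.** The paragraph opens by describing death as the outcome of an SAE, so it may reach SAEs only. That narrows the conflict but does not remove it. The seriousness criteria in 8.5.2 include hospitalization and medical significance, and neither is a grade.

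**3. Effect on the grade tables**

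| True grade | Assigned | Grade 3/4 count | Grade 4 column |
|---|---|---|---|
| 1 or 2 | 4 | event added | event added |
| 3 | 4 | unchanged | event added |
| 4 | 4 | unchanged | unchanged |

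No row lowers a count, so the bias is upward or nil. In the per-patient rows of Table 12.2.1.1, a patient is added only if the true grade was 1 or 2 and the patient has no other grade 3/4 event that qualifies for that row. The SAP plans no flag and no sensitivity display for grades assigned by outcome.

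**4. Size per affected patient.** Let k be the number of patients who enter a grade 3/4 row only because of this rule, among N treated. The shift is 100 × k / N percentage points. Taking N = 60 from Protocol 9.1:

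- k = 1: 100 × 1/60 = 1.7 points
- k = 3: 100 × 3/60 = 5.0 points
- k = 6: 100 × 6/60 = 10.0 points

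The documents do not give k; the three values only show scale. The safety set is all treated patients, which can exceed 60 because unconfirmed cases are supplemented by additional patients (Protocol 5.3). The step per patient would then be somewhat smaller.

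**5. Effect on the fatal-event displays.** If a display is derived from Grade 5, the Grade 4 instruction adds 0 events, because it keeps non-causal events out of Grade 5. If a display is derived from outcome of death, as in SAP 7.1, non-causal events with that outcome are included, and would be included at any grade. The cause there is the outcome coding, not the grade.

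**6. What is not reached.** SAP 7.2 grades laboratory abnormalities from the results, so those tables do not change. Response rate, sample size and futility boundaries do not use AE grade.

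**The case against.** The strongest reply is that the rule has a narrow reach. It applies only to events already coded with an outcome of death, and no text tells sites to code an incidental, ongoing event that way. Section 8.5.3 asks instead for the cause of death to be the SAE term. It says should, not must, and it may concern SAEs only. The outcome options on the CRF are not in the documents. SAP Listing 12.3.1.5 shows status, grade, relationship and seriousness criteria for each SAE, narratives are planned, and Table 12.3.2.1 reports cause of death separately.

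Most of this stands and limits the point. It does not remove it. The sentence on Grade 4 presupposes that non-causal events can carry an outcome of death; otherwise it would have nothing to apply to. The SAE listing has a single grade column, so it shows the assigned Grade 4 and not the severity it replaced. Narratives may let a reader spot a case, but they do not correct the counts.

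Three stronger readings are tempting and are not supported:

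- A reader might infer that the Grade 4 instruction inflates the count of AEs leading to death. It does not, as step 5 of the working shows.
- A reader might infer that any mild event still present when a patient dies of lymphoma becomes Grade 4. The text reaches only events coded with a fatal outcome.
- A reader might try to project a number of affected patients from the survival figures of the earlier PTCL cohort (Protocol Table 1). Those figures bear on how many patients die. They do not give the share of deaths with a non-causal event coded fatal, or the share of those patients who already have another grade 3/4 event.

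**Conclusion.** The contradiction is real and stands whatever its size: for non-causal events with a fatal outcome, 8.5.3 replaces the severity grade that 8.2, 8.6.1 and 9.2.2 require. The grade 3/4 AE and SAE counts can be biased upward but not downward. The size is about 1.7 percentage points for each affected patient, assuming 60 treated patients, a true grade of 1 or 2, and no other grade 3/4 event in that patient. Inflation is possible, not certain, and the number of affected patients cannot be derived from the documents.

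The fatal-outcome display in SAP 7.1 can include events that did not cause death. This is a separate matter that comes from outcome coding together with selection by outcome. The row in Table 12.2.1.1 and Listing 12.3.2.3 are undefined on the point; their labels are causal, but no derivation is given.

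**What to change.** In Protocol 8.5.3, replace the Grade 4 sentence so that it agrees with 8.2 and 8.6.1. An event that did not cause the death keeps the NCI-CTCAE grade of its own severity, with an outcome such as not recovered at time of death. The outcome death, together with Grade 5, is kept for the event that caused the death.

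In the SAP, state that the fatal-event display in 7.1, the corresponding row of Table 12.2.1.1 and Listing 12.3.2.3 are all derived from those causal, Grade 5 events.

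The cost is one protocol sentence, an edit to the CRF completion guideline, one SAP line, and queries on any entries already made under the present rule. No new data are needed.

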### **8.5.4 Life-threatening Event**

Any event in which the patient was at risk of death at the time of the event is considered life-threatening; it does not refer to an event which hypothetically might have caused death if it were more severe.

### **8.5.5 Hospitalization or Prolongation of Hospitalization**

Any AE requiring hospitalization (or prolongation of hospitalization) that occurs or worsens during the course of a patient's participation in a clinical trial must be reported as a SAE unless exempted from SAE reporting. Prolongation of hospitalization is defined as any extension of an inpatient hospitalization beyond the stay anticipated/required for the initial admission, as determined by the Investigator or treating physician.

Hospitalizations that do not meet the criteria for SAE reporting are:

- a. Reasons described in the protocol [e.g., investigational medicinal product (IMP) administration, protocol-required intervention/investigations, etc.]. However, events requiring hospitalizations or prolongation of hospitalization as a result of a complication of therapy administration or clinical trial procedures will be reported as SAEs.
- b. Hospitalization or prolonged hospitalization for technical, practical or social reasons, in the absence of an AE.
- c. Pre-planned hospitalizations: any pre-planned surgery or procedure must be documented in the source documentation. Only if the pre-planned surgery needs to be performed earlier due to a worsening of the condition, should this event (worsened condition) be reported as a SAE.

Other situations that **MUST NOT** be considered as hospitalizations are the following:

- d. An emergency visit due to an accident where the patient is treated and discharged.
- e. When the patient is held 24 hours for observation and finally is not admitted.
- f. Planned treatments at sites not associated to a hospital and generally considered as minor surgical procedures (i.e., laser eye surgery, arthroscopy, etc.).

### **8.5.6 Unlisted/Unexpected Adverse Event**

An AE, the nature or severity of which is not consistent with the applicable reference safety information.

The Sponsor will use as the reference safety information for the evaluation of listedness/expectedness the most updated IB for plitidepsin.

### **8.5.7 Adverse Reactions**

All untoward and unintended responses to an investigational medicinal product related to any dose administered. This definition covers also medication errors and uses outside what is foreseen in the protocol, including overdose, lack of efficacy, misuse and abuse of the product.

